blinded to treatment condition and time of assessment, using the Clinician Global Assessment Scale [CGAS]⁶¹ in more children in the “*Taming Sneaky Fears for SAD and/or SM*” than children in the comparison group at post-intervention and at 6-month follow-up. A ≥10 point change means change from one category to the next on the CGAS.

A second objective of this study is to evaluate parent and teacher ratings of child symptomatology (SAD and SM) at home and in the classroom, respectively, over the course of the treatment program.

Hypothesis #4: Parents of children who attend the “*Taming Sneaky Fears for SAD and/or SM*” will report significantly fewer symptoms over the course of the study than those in the “Parent Psycho-education and Child Socialization” as measured by the parent Selective Mutism Questionnaire (SMQ)⁶² and the Social Anxiety Scale for Children Revised for Parents (SASC-P).⁶³ Similarly, teachers will report significantly fewer symptoms over the course of this study in children who attend the “*Taming Sneaky Fears for SAD and/or SM*” than those in the “Parent Psycho-education and Child Socialization,” as measured by the teacher School Speech Questionnaire (SSQ)⁶⁴ and the Social Anxiety Scale for Children Revised for Teachers (SASC-T).⁶³

A third objective is to explore factors within the child, parent and environment that predict treatment outcome (i.e., loss of at least one anxiety diagnosis post-treatment; this objective could not be explored in the original OMHF study due to the small sample size and lack of power). Factors hypothesized to predict treatment outcomes include within-the-child factors (age, gender, BI, and speech-language difficulties) and within-the-parent/environment factors (family history of SAD or SM, immigration status, and family stresses).

Hypothesis #5: The most significant factor to predict treatment outcome (i.e. lost diagnosis) at 6 months will be treatment group. The other factors (age, gender, BI, speech-language difficulties, family history of SAD or SM, immigrations status, family stresses) will not be significant in predicting treatment outcome.

METHODS:

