Sample Size Calculation is based on data from our previous OMHF study, showing that 42% of children in the “*Taming Sneaky Fears*” program lost their primary diagnosis of SAD and/or SM post-intervention vs. none of the children in the comparison group (using the ADIS-P). In the present study, we conservatively estimate that 10% of children will lose their SAD and/or SM diagnosis in the comparison group. Hence using this difference of 32% (42% - 10%), a sample size of 69 (to round up, 35 subjects per treatment protocol) would achieve a power of 81% to detect a difference of 32% between treatment programs using a two-sided Chi-squared test with continuity correction with a significance level set at 0.05.⁶⁵ Further, a total of 15/77 children (19%) did not complete the full protocol in the original OMHF study, so we anticipate a 20% (n=18) dropout rate over the course of this study. As a result, 88 participants need to be recruited to ensure a final sample size of 70. In order to obtain a sample size of 88

participants over two years, 2 sites are necessary.

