To address Hypothesis 1, we will use a two-sided Chi-Square test with continuity correction to compare the difference between the two 2 groups in the proportion of children who lost diagnoses post-treatment (T2) and 6 months post-treatment (T3).

To test Hypothesis 2, we will use a repeated measures regression model on the ADIS-CSR and compare the two 2 treatment groups from pre-treatment (T1) to 6-month post treatment (T3). An interaction term between time and group will be introduced in the model in order to explore possible differences at different time points between the two groups. The assumptions of the model will be verified using residual analysis and, if necessary, transformations will be used in order to obtain a valid model. This repeated measures regression model will be used for Hypotheses 3 and 4 to assess child global functioning using CGAS and parent and teacher reports of child symptoms on SMQ, SASC-P/T and SSQ.

To examine Hypothesis 5, a logistic regression analysis will be employed. This will allow for the examination of the strength of multiple predictors on the likelihood that a child will lose an anxiety disorder diagnosis 6 months post-intervention (T3). The predictor factors that will be included in this model include group intervention (“*Taming Sneaky Fears for SAD and/or SM*” or “Parent Psycho-education and Child Socialization”), within-the-child factors (child’s age, sex, BI, and speech-language difficulties), parent factors (family history of SAD or SM), and environmental factors (family stress, immigration status). All the significant factors will be put into the model and non-significant predictors will be excluded. The model will control for age and sex of the child.

ORIGINALITY AND SIGNIFICANCE/RELEVANCE: This is the first RCT to assess the efficacy of “*Taming Sneaky Fears for SAD and/or SM*”, a group CBT treatment approach to treat 4 to 7 year old children with SM and/or SAD, which are anxiety disorders affecting as many as 36,340 children under age 14 in Ontario. The present study addresses methodological shortcomings of previous studies and builds on OMHF-funded previous work while addressing a significant clinical problem for which little convincing evidence for treatment efficacy exists. The present study represents an innovative treatment method that is brief, CBT-based, and group-focused.

Timeline of the Study:

REFERENCES

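### Hypothesis 5's selection rule does not protect the treatment arm, and the planned logistic regression has no finite arm estimate if no comparison child loses the diagnosis

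*Combined protocol and SAP*

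**What the plan says.** The Statistical Analysis and Data Analyses Plan says: "To examine Hypothesis 5, a logistic regression analysis will be employed". The outcome there is the "likelihood that a child will lose an anxiety disorder diagnosis 6 months post-intervention (T3"). The third objective words it as "loss of at least one anxiety diagnosis post-treatment".

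On predictors, the plan says "The predictor factors that will be included in this model include group intervention", and goes on to list age, sex, behavioural inhibition, speech-language difficulties, family history, family stress and immigration status. The selection rule follows: "All the significant factors will be put into the model and non-significant predictors will be excluded". The only terms stated as controlled for are in the last sentence: "The model will control for age and sex of the child". The plan names no selection test (Wald, likelihood ratio or score), no threshold, and no procedure for a cell without events.

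Hypothesis #5 itself predicts: "The most significant factor to predict treatment outcome (i.e. lost diagnosis) at 6 months will be treatment group".

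**The concern.** Hypothesis 5 is mainly a statement about treatment arm, yet the rule allows arm to be removed from the model that tests it. Age and sex are protected; arm is not.

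The choice of test matters most when the comparison arm has no events. Ordinary maximum likelihood then has no finite estimate for arm (separation): the log odds ratio grows at each iteration, its standard error grows faster, and the Wald statistic falls towards zero. Under Wald selection, arm would be excluded as non-significant in the data that support Hypothesis 5 most strongly. Because the test is unnamed, the analyst would have to choose it, or a substitute method, after seeing the empty cell.

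A low comparison rate is not far-fetched. The Sample Size Calculation reports that no child in the earlier comparison group lost the primary diagnosis post-intervention. The Background says that childhood anxiety disorders rarely remit untreated.

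**Working it through.** **Inputs.** From the Sample Size Calculation: 35 per arm in the final sample, 42% v 10%, two-sided 0.05, 20% dropout. From Feasibility of the Study: 10/24 (42%) lost the diagnosis post-intervention in the earlier active arm, and 16/24 (67%) by 6 months. Assumed here: 35 per arm observed at T3, and selection at 0.05.

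**The plan's own figure.** No sample size is given for Hypothesis 5. The figure for Hypothesis 1 reproduces. With continuity correction, power is Φ{[0.32 − 1/35 − 1.96·√(2·0.26·0.74/35)] / √[(0.42·0.58 + 0.10·0.90)/35]} = Φ(0.0859/0.0976) = Φ(0.88) = 81%. Recruitment is 70/0.80 = 87.5, so 88.

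**Chance of an empty comparison cell**, (1 − r)^35:

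| True comparison rate r | P(0 of 35) |
|---|---|
| 10% (planned) | 2.5% |
| 5% (assumed) | 17% |
| 2% (assumed) | 49% |

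**What each test does.** 15/35 is close to 42% and 23/35 is close to 67%. The Wald column shows p after 8 and after 25 iterations where the fit does not converge.

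| Active v comparison | Wald p | Likelihood-ratio p | Corrected chi-square p |
|---|---|---|---|
| 15 v 0 | 0.60, then 1.0 | 6e-7 | 5e-5 |
| 23 v 0 | 0.56, then 1.0 | 4e-11 | 2e-8 |
| 15 v 1 | 0.0025 | 2e-5 | 2e-4 |
| 23 v 1 | 0.0001 | 2e-9 | 1e-7 |

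For 23 v 0, the likelihood-ratio statistic is 2·{[23 ln(23/35) + 12 ln(12/35)] − [23 ln(23/70) + 47 ln(47/70)]} = 2·(−22.50 + 44.32) = 43.6 on 1 degree of freedom. A single comparison event removes the failure.

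**How often arm would be dropped.** 2,000 simulated trials per scenario; model with arm, age and sex; age and sex unrelated to outcome:

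| True rates | Dropped, Wald | Dropped, likelihood ratio |
|---|---|---|
| 42% v 10% | 13% | 9% |
| 42% v 5% | 18% | 2% |
| 67% v 10% | 2.6% | 0% |
| 67% v 5% | 16% | 0% |

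Given an empty comparison cell, Wald selection dropped arm every time and likelihood-ratio selection never did. The 9% in the first row is ordinary sampling variation: an unprotected arm can be lost without any separation.

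**Separation from other predictors.** Speech and Language Testing defines four categories. Full predictor set, n = 70, 1,000 trials per scenario, comparison rate 10%. Assumed: speech-language splits of 50/20/15/15 or 60/20/10/10, family history 30%, immigration 25%, no true covariate effects. If all four categories are modelled, some term separates in about 7–18% of trials at 67% v 10% and 17–35% at 42% v 10%. If the factor is coded yes/no, this falls to about 3–5%, most of which is the empty comparison cell.

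**Firth's penalised fit on the same tables.** 15 v 0: odds ratio about 54, penalised likelihood-ratio p = 3e-6. 23 v 0: odds ratio about 134, p = 3e-10.

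**The case against.** Four points can be made for the plan.

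*The reversal needs a Wald test that the plan never names.* This stands. The selection sentence can be read as screening each factor first, and the only test named for arm against lost diagnosis is the corrected chi-square of Hypothesis 1, which keeps arm in both empty-cell examples. A reader might infer that the plan as written would discard arm; the documents leave that possible but do not establish it.

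*The earlier zero is not a forecast for T3.* This also stands. The Sample Size Calculation gives it as "post-intervention vs. none of the children in the comparison group (using the ADIS-P"): a post-intervention result for the primary diagnosis. Hypothesis 5 concerns 6 months, and its outcome is worded more broadly, so an empty cell is less likely. The comparator differs too: earlier comparison parents received CBT (Previous Work in Our Lab), whereas here they do not (Study Design), which points the other way. A reader might infer that the sponsor's own data make an empty cell likely; no T3 comparison rate is given to support that, and the plan assumes 10%.

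*Covariate separation is a different matter.* Agreed. It rests on assumed splits and on modelling all four speech-language categories, which the plan does not say it will do. It leaves that factor's odds ratio without a finite estimate. It does not reverse the test of arm, and Hypothesis 5 predicts no effect of these factors anyway.

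*The consequence is limited and easily repaired.* Hypothesis 5 serves an exploratory third objective, and Hypothesis 1 tests arm at T3 by a method that works with an empty cell. That limits the harm. But switching method after seeing the empty cell would be post hoc, and the lack of protection for arm does not depend on an empty cell at all.

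It could also be said that arm is listed among the predictors to be included. So is every other candidate, and the exclusion rule then applies to all of them.

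**Conclusion.** The concern holds as a gap in specification with a conditional failure attached. What is certain from the text is that arm, the term Hypothesis 5 is about, can be excluded by an unnamed test while only age and sex are protected. What is conditional is the reversal: it needs no events among the comparison children at T3 (2.5% at the planned rate, 17% at an assumed 5%, with 35 per arm) and selection by Wald p-value. Separation in the speech-language factor is a secondary estimation problem whose frequency depends on coding and on prevalences the documents do not give. It should be settled before the analysis, but it does not touch the primary analysis or the sample size.

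**What to change.** In the Hypothesis 5 paragraph of the Statistical Analysis and Data Analyses Plan, replace the selection rule as it applies to arm, age and sex, and name the method:

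> Group intervention, age and sex stay in the model whatever their p-values. The model will be fitted by Firth penalised-likelihood logistic regression, with penalised likelihood-ratio tests (not Wald) and profile-likelihood intervals.

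The cost is two sentences and a standard software option, with slight shrinkage of the odds ratios. The sample size stays at 70 final and 88 recruited. Naming Firth only as a fallback for an empty cell would also prevent a post hoc choice, but using it throughout avoids a data-dependent switch and covers sparse speech-language levels as well.

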Recruitment: Children referred for an assessment of SAD and/or SM at either site are assessed by 1 of the 4 child psychiatrists, who obtains information about presenting problem, its impact on the child's functioning at school, home and with peers, and developmental, medical and family history. Eligible, interested children and families meet with a Clinical Research Project Coordinator (coordinator) who describes the study immediately post-assessment at either HSC or TEGH (depending on site where child was assessed). The coordinator obtains informed consent from parent(s) and assent from child, gives pre-treatment questionnaires to the parent(s), and schedules the first research assessment visit (Time 1) at HSC within 2 to 3 weeks of assessment and start of treatment group. Children and families not eligible for the study or who decline to participate are treated or referred for appropriate treatment as usually done in each clinic.

Measures: A demographic questionnaire (child's age and gender, parent's name, family composition, family history of SAD or SM, and immigration status) is completed by the parent at the start of the study.

A. Clinician Rated Measures:

- 1) The Anxiety Disorders Interview Schedule for DSM-IV, Parent Version (ADIS-P)⁵⁹ is used to assess SAD and/or SM. The ADIS-P has good reliability,⁶⁶ is sensitive to treatment effects in child anxiety studies,^{66,67} and has been used in a number of studies on preschoolers^{45,46,48} and SM treatment.⁵⁸ Clinical Severity Rating (ADIS-CSR) uses a 0 to 8 scale to measure clinical severity of diagnosis; a CSR of ≥ 4 indicates clinically significant symptoms and presence of an anxiety disorder. A trained independent clinician blinded to treatment type and time of assessment completes the CSR.
- 2) The Children's Global Assessment Scale (CGAS)⁶¹ assesses adaptive functioning during the previous month for children aged 4-16 years. It has high inter-rater and test-retest reliability. A trained independent clinician blinded to treatment type and time of assessment completes the CGAS.

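### Hypothesis 5 examines its predictors only on lost diagnosis at T3; a model of the 0 to 8 ADIS-CSR already collected should be pre-specified beside it, with confidence intervals

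*Combined protocol and SAP*

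**What the plan says.** **Outcome.** The third objective, under Research Questions and Hypotheses, defines treatment outcome as "loss of at least one anxiety diagnosis post-treatment". Hypothesis 5 there speaks of lost diagnosis at 6 months. The Statistical Analysis and Data Analyses Plan tests Hypothesis 5 by logistic regression, for "examination of the strength of multiple predictors on the likelihood that a child will lose an anxiety disorder diagnosis 6 months post-intervention (T3"). The listed predictors are group, age, sex, behavioural inhibition, speech-language difficulties, family history, family stress and immigration status. Predictors that are not significant are then dropped.

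**Prediction.** Treatment group is expected to be the strongest predictor. The other factors "will not be significant in predicting treatment outcome".

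**The underlying score.** The ADIS-P entry under Clinician Rated Measures says the CSR "uses a 0 to 8 scale to measure clinical severity of diagnosis" and that "a CSR of ≥ 4 indicates clinically significant symptoms and presence of an anxiety disorder". The section on the T2 and T3 assessments has an assessor blinded to treatment group carry out these ratings. For Hypothesis 2 the score is kept whole: "we will use a repeated measures regression model on the ADIS-CSR and compare the two 2 treatment groups from pre-treatment (T1) to 6-month" follow-up.

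**Power.** The third objective exists because "this objective could not be explored in the original OMHF study due to the small sample size and lack of power". The Risk Factors section says the present sample has the power needed to examine the factors together. The only calculation, under Sample Size Calculation, is for the two-arm comparison of lost diagnosis.

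**The concern.** If a disorder is present at a CSR of 4 or more, losing the diagnosis means falling below 4. A child who goes from 8 to 4 then counts the same as one who does not change, and a child at 3 counts the same as one at 0. When a factor moves severity along the whole scale, discarding that detail lowers the chance of detecting it.

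The direction of the loss is what matters here. Hypothesis 5 is borne out when seven of its eight predictors are non-significant, so low power favours the plan's own prediction. A reader could take a null result as evidence that age, inhibition or language skills do not affect outcome when the model had little chance of showing that they do.

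**Working it through.** **1. The plan's own figure.** Inputs from Sample Size Calculation: 42% v 10%, two-sided 0.05, continuity-corrected chi-squared, 81% power. The mean proportion is (0.42 + 0.10)/2 = 0.26.

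- Uncorrected n per arm = [1.96·√(2·0.26·0.74) + 0.878·√(0.42·0.58 + 0.10·0.90)]² / 0.32² = (1.216 + 0.507)² / 0.1024 ≈ 29.
- Corrected n = (29/4)·[1 + √(1 + 4/(29·0.32))]² ≈ 35.
- Recruitment = 70/0.80 = 87.5, so 88.

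The stated 35 per arm, 81% and 88 reproduce. They concern Hypothesis 1. There is no figure for Hypothesis 5 to reproduce.

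**2. Expected events for Hypothesis 5.** The CBT rate at 6 months is 67% (16/24 in the earlier study, Feasibility of the Study). No comparison-arm rate at T3 is given; 10% (the sample-size assumption for post-intervention) to 30% is assumed.

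- At 10%: 35·0.67 + 35·0.10 = 23.45 + 3.5 ≈ 27 losses of diagnosis, or 27/8 ≈ 3.4 per predictor.
- At 30%: 23.45 + 10.5 ≈ 34, or 34/8 ≈ 4.2 per predictor.

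**3. Power with and without the cut, roughly normal severity.** Assumed, not in the documents: latent SD 1.8 CSR points, rounded and limited to 0–8; one binary factor shifting severity by 0.5 SD (0.5·1.8 = 0.9 points) or 0.75 SD (1.35 points). The design has 70 children, 35 per arm, with eight predictors in both models. The logistic Wald test on CSR < 4 is compared with linear regression on CSR with HC3 errors, at 3,000 simulated trials per row (standard error at most √(0.25/3000) ≈ 0.9 points).

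| Comparison rate | Children with factor | Shift | Logistic | CSR model | Gain (points) |
|---|---|---|---|---|---|
| 10% | 50% | 0.5 SD | 26% | 41% | 15 |
| 10% | 50% | 0.75 SD | 52% | 76% | 24 |
| 10% | 25% | 0.5 SD | 20% | 32% | 12 |
| 10% | 25% | 0.75 SD | 37% | 64% | 27 |
| 30% | 50% | 0.5 SD | 33% | 42% | 9 |
| 30% | 50% | 0.75 SD | 62% | 78% | 16 |
| 30% | 25% | 0.5 SD | 26% | 33% | 7 |
| 30% | 25% | 0.75 SD | 50% | 65% | 15 |

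A latent SD of 1.4 or 2.2 moves these by at most about 4 points. A repeat at 1,200 trials per setting gave gains of about 6 to 28 points against the Wald test and 3 to 22 against the likelihood-ratio test. A separate set with conventional errors gave about 7 to 28 against the likelihood-ratio test.

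**4. False positives.** At zero effect the Wald test rejected about 5–6% and the CSR model 3–4.5%, so the gain is not bought with type I error.

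**5. Where the gain shrinks or reverses.**

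- Shift of 0.3 SD, normal, HC3: 14% v 17% (comparison 10%) and 15% v 16% (30%). With conventional errors the gain was about 3 to 7 points against the likelihood-ratio test, and up to 10 in one setting against the Wald test.
- Heavy tails (t, 4 df), 0.5–0.75 SD: 13 to 23 points at 10%, but 1 to 6 at 30%.
- Moderate skew (gamma, shape 4), 0.5–0.75 SD: 3 to 24 points. A right-skewed shape in the separate set: −9 to +13 (likelihood-ratio), the −9 at rates of 42% and 10%.
- Exponential shape, 0.5 SD, comparison 10%: 65% (likelihood-ratio) v 51%, a loss of 14 points.
- Factor acting only on whether the diagnosis is lost, with CSR scattered on either side of the cut: the CSR model loses about 2 to 19 points (likelihood-ratio). At 67% and 10% with eight predictors and effect 0.5, for example, it is 30% v 19%.

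None of these runs includes the T1 CSR as a covariate or the plan's significance-based selection.

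**The case against.** Lost diagnosis is the trial's primary outcome, and asking which children achieve it is a coherent and clinically readable question. If factors work on remission itself, the logistic model is the more powerful one, and nothing in the documents shows which mechanism applies. This stands, and it is why the logistic model should stay.

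The CSR is also not simply the same outcome uncut. The wording ranges over primary diagnosis, an anxiety disorder diagnosis and at least one diagnosis. SAD and SM often occur together, so a child may carry more than one CSR, and the plan does not say which is modelled for Hypothesis 2. This stands too, and the score must be named.

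A raw T3 score would partly reflect where a child started, so a T1 term is needed. Nor does a finer outcome cure low power: at 0.5 SD the CSR model still reaches only 32% to 42%. Reading non-significance as support would remain unsafe, so intervals matter as much as the change of scale.

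A reader might infer that a large loss applies to every factor under most distributions and reverses only in an extreme case. The documents give no spread, shape or effect to support that, and step 5 contradicts it. Nor does the range extend to treatment group, whose assumed effect is far larger and whose loss was not simulated.

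**Conclusion.** The point holds as a cheap improvement, not as an error in the choice of outcome. Hypothesis 5 relies on a single yes/no outcome although a blinded, finer score is available for the same children at the same visit.

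Under one explicit set of assumptions (70 analysed, eight predictors, 67% v 10% to 30%, roughly normal severity, a shift of 0.5 to 0.75 SD from a factor other than group) the cut costs about 7 to 28 points of power, somewhat less against a likelihood-ratio test with robust errors. At 0.3 SD it costs about nil to 8 points. It is often small with skewed or heavy-tailed severity, especially at 30%, and the sign can turn with strong skew or a remission-only factor. All of this rests on quantities that the documents do not give.

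It matters because the plan predicts null results for seven factors with about 27 expected losses of diagnosis. It would go too far to conclude that lost diagnosis should be demoted or Hypothesis 5 reworded. Hypothesis 1 and its sample size are unaffected; those figures reproduce.

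**What to change.** In the Hypothesis 5 paragraph of the Statistical Analysis and Data Analyses Plan:

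- Keep the logistic model for lost diagnosis at T3.
- Pre-specify beside it a linear regression of the T3 ADIS-CSR of the child's primary SAD/SM diagnosis on the same full list of predictors plus the T1 CSR, with robust (HC3) errors and no removal of predictors by significance.
- State which CSR is used when a child has both SAD and SM.
- Report each coefficient in CSR points with a 95% CI. Base any statement that a factor does not predict outcome on what those intervals exclude, not on non-significance alone.

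The cost is a few sentences and one more model on data already collected, with no new children, visits or staff. The downside is a second result, in CSR points rather than odds of losing the diagnosis, which may not agree with the first.

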RESEARCH QUESTIONS AND HYPOTHESES TO BE TESTED: This study builds on our previous OMHF funded work in which we demonstrated that 5 to 7 year old children with anxiety disorders randomized to the “*Taming Sneaky Fears*” group CBT program exhibited greater improvements in global functioning and lost more diagnoses than those randomized to the parent only group CBT program. Starting with a previously proven treatment protocol that is engaging and teaches young children various CBT strategies, we use a slightly revised and refined treatment protocol specifically for children with SAD and/or SM and their parents and expand the age range down to 4 years. The primary objective of this study is to assess the efficacy of the brief (10 concurrent parent and child + 1 parent only), refined, group CBT program “*Taming Sneaky Fears for SAD and/or SM*” in the treatment of 4 to 7 year old children with SAD and/or SM.

Hypothesis #1: The “*Taming Sneaky Fears for SAD and/or SM*” group CBT treatment is more efficacious than a comparison intervention, “Parent Psycho-education and Child Socialization” such that more children in the “*Taming Sneaky Fears for SAD and SM*” group CBT will lose their primary diagnosis of SAD and/or SM, compared to children in the comparison group. Our primary outcome measure will be loss of diagnosis of SAD and/or SM as assessed by an independent clinician blinded to treatment condition and time of assessment using a semi-structured interview, the Anxiety Disorders Interview Schedule for Parents [ADIS-P]),⁵⁹ post-intervention and at 6-month follow-up.

Hypothesis #2: In those children who do not lose their primary diagnosis of SAD and/or SM, there will be a 2.0 or greater point improvement in anxiety severity (measured by an independent assessor blinded to treatment condition and time of assessment, using the ADIS-P Clinical Severity Rating [ADIS-CSR]) in more children in the “*Taming Sneaky Fears for SAD and/or SM*” program than children in the comparison group at post-intervention and at 6-month follow-up. This hypothesis is based upon a recent meta-analysis that suggests a 2.0 change in the ADIS-CSR is a clinical meaningful change.⁶¹

Hypothesis #3: In those children who do not lose their primary diagnosis of SAD and/or SM, there will be a 10.0 or greater point improvement in global functioning (measured by an independent assessor

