Study Design: This study utilizes a repeated measures, longitudinal, randomized controlled trial design to compare the efficacy of two interventions in the treatment of children aged 4 to 7 years with SM and/or SAD. Participants are randomized into either the (1) “*Taming Sneaky Fears for SAD and/or SM*” parent and child group CBT treatment, or (2) the “Parent Psycho-education and Child Socialization” comparison program. Both programs run for 10 consecutive weeks (plus one additional introduction week). To control for the nonspecific factors associated with treatment, such as the support, attention and expectation of improvement, parents and children in both treatment protocols receive comparable levels of attention from therapists (i.e., same duration of group sessions and total number of sessions with a therapist) and comparable opportunities for socialization (e.g., for the children: invitation to discuss how the previous week went, snack time, story time; for the parents: discussion of specific topics at each session). However, parents and children in the comparison group are not taught CBT strategies.

Participants:

Inclusion Criteria: 4 to 7 year old children referred for psychiatric assessment of SM and/or SAD who meet diagnostic criteria for SM and/or SAD as a primary diagnosis, as determined by 1 of the 4 psychiatrists at the 2 sites where the study is conducted. Presence of other anxiety disorders/symptoms is not an exclusion criterion as long as the main concern is SAD and/or SM.

Exclusion Criteria: Presence of autism spectrum disorder, brain injury, or significant developmental delays (based on medical history and clinical assessment). Children and parents not fluent in English.

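### Hypothesis 5 keeps predictors by significance with about 27 to 30 expected events, so real factors are often dropped and the surviving odds ratios are too large, mainly for binary factors

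*Combined protocol and SAP*

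**What the plan says.** The Statistical Analysis and Data Analyses Plan assigns a logistic regression to Hypothesis 5. The predictors are arm, age, sex, behavioural inhibition (BI), speech-language difficulties, family history, family stress and immigration status. The selection rule is "All the significant factors will be put into the model and non-significant predictors will be excluded", and the next sentence adds "The model will control for age and sex of the child". No retention threshold or test is named, and nothing says whether factors are screened one at a time or together. The 0.05 level in the Sample Size Calculation belongs to the Hypothesis 1 test.

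Hypothesis 5 expects treatment group to be the strongest predictor at 6 months and says that the other seven factors "will not be significant in predicting treatment outcome". The objective is worded as exploratory: "A third objective is to explore factors within the child, parent and environment that predict treatment outcome".

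Item c (Risk Factors) of the Background asserts that the sample gives adequate power to study several child and family factors together. The Problem section and the Feasibility of the Study section (in two places) also link the sample size to studying these factors. The Sample Size Calculation covers only 42% versus 10% between arms.

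The outcome is described in several ways:
- Third objective: "loss of at least one anxiety diagnosis post-treatment".
- Hypothesis 5: a lost diagnosis at 6 months.
- Analysis plan: "likelihood that a child will lose an anxiety disorder diagnosis 6 months post-intervention (T3").
- Hypothesis 1: children who "will lose their primary diagnosis of SAD and/or SM".

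**The concern.** Selection by p-value with few events does harm in two ways. A real factor usually fails the test and disappears from the report. A factor that passes tends to do so because its estimate happened to be high, so the published odds ratio is too large. Hypothesis 5 makes non-significance the predicted finding, so low power alone can make the prediction look confirmed. Conversely, with seven tests, one null factor may well be reported as a predictor. At stake is what clinicians are told about which children respond.

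**Working it through.** **The plan's own figure.** For 42% versus 10% the mean proportion is 0.26. At two-sided 0.05 and 81% power (z = 1.960 and 0.878), the uncorrected n per arm is [1.960·√(2·0.26·0.74) + 0.878·√(0.42·0.58 + 0.10·0.90)]² / 0.32² = 29.0. With continuity correction, n = (29.0/4)·[1 + √(1 + 4/(29.0·0.32))]² = 35.0 per arm, or 70 in total. Dropout of 20% gives 70/0.80 = 87.5, so 88. The stated figures reproduce. There is no corresponding figure for Hypothesis 5.

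**Expected events at T3.** The active-arm rate is 16/24 = 67% (Feasibility of the Study: 10 children, then 6 more). The only comparison rate is 10%, a post-intervention planning value, so carrying it to T3 is an assumption.

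| Comparison rate | Events = 35·(16/24) + 35·rate |
|---|---|
| 0% | 23.3 |
| 10% | 26.8 |
| 20% | 30.3 |
| 30% | 33.8 |

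**Parameters.** Arm plus seven factors is 8 with speech-language as one term. Speech and Language Testing records four categories, and entering these needs three terms, making 10. At 26.8 events this is 26.8/10 = 2.7 to 26.8/8 = 3.4 events per parameter.

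**Simulation of the stated procedure.** Factors were screened at 0.05 (Wald), then the model was refitted with arm, age, sex and the survivors. Assumptions: 35 per arm, comparison rate 10% or 20%, independent covariates, standard normal continuous factors. At 2,000 runs, the standard error of a proportion near one half is √(0.25/2000) = 0.011, so the percentages are good to about two points.

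| Factor, true odds ratio 2 | Kept | Median reported odds ratio | Ratio to truth |
|---|---|---|---|
| Balanced binary | 18-24% | 4.6-6.4 | 2.3-3.2 |
| Continuous, per SD | 53-63% | 2.6-2.9 | 1.3-1.5 |

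If only a quarter of children have the binary factor, the ratio is about 3-4.

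**Threshold.** Screening at 0.20 keeps the balanced binary factor in about 37-48% of trials, with a reported odds ratio of about 3.4-4.1 (3.4/2 = 1.7 to 4.1/2 = 2.1 times the truth). The inflation is smaller but still material.

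**All seven factors null.** With independent tests, 1 − 0.95⁷ = 0.302. Simulated full-model Wald fits give about 30%; likelihood-ratio tests give 39-43%, because they are somewhat liberal at this size.

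**Hypothesis 5 looks confirmed although one factor has an odds ratio of 2.** Across Wald and likelihood-ratio tests, fitted jointly or one at a time with arm, all seven are non-significant in 46-64% of trials if that factor is binary and 22-38% if it is continuous.

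**Detectable size at 80% power.** This is an odds ratio of about 6 for a balanced binary factor (power at 6: 69-87%) and below 3 per SD for a continuous factor (71-86% at 2.5, 82-95% at 3). The two agree on one scale: a balanced binary factor has SD 0.5, and 6^0.5 = 2.45 per SD.

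**Outcome wording.** The third objective differs from Hypothesis 1 on diagnosis (any anxiety diagnosis against primary SAD/SM). It also differs from Hypothesis 5 and the analysis plan on time, because the analysis plan labels post-treatment as T2 and 6 months post-treatment as T3. The diagnosis matters because of the inclusion criteria: "Presence of other anxiety disorders/symptoms is not an exclusion criterion as long as the main concern is SAD and/or SM". The time point matters because T2 rates give only 35·0.42 + 35·0.10 = 18.2 events.

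**The case against.** The strongest reply is that this objective is exploratory and that the plan states no rule for concluding that a factor has no effect. Both points are correct. A reader might infer that the plan will treat non-significance as proof of no effect, but the documents do not say so. What remains is that Hypothesis 5 is numbered and directional, it predicts non-significance, and Risk Factors claims power for these factors. An exploratory aim is served by estimates with intervals, which the selection rule discards.

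Three other limits stand:
- A reader might infer that all seven factors can be dropped. Age and sex are forced in, so selection acts on BI, speech-language, family history, stress and immigration status. As written it also acts on arm, which the sentence does not exempt.
- A reader might take odds ratios from the full model, which put the inflation for a balanced binary factor at up to about four times (medians up to 8.5). The plan would report the reduced model, where the range is 2.3-3.2.
- The binary-continuous contrast is partly one of scale. For a strong continuous factor a non-significant result does carry some information.

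The event count rests on 24 earlier children and an assumed T3 comparison rate. The pattern was the same over 18 to 34 events.

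**Conclusion.** The concern holds for the third objective and should be corrected. Under the stated assumptions (70 children, 27-30 events, independent covariates, Wald tests at 0.05), the rule drops a balanced binary factor that truly doubles the odds in about four trials in five. When it keeps that factor, it reports two to three times the true odds ratio. Continuous factors suffer less. The principle is secure; the exact figures depend on prevalence, threshold and event rates that the plan does not fix.

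A reader might infer that the trial's main result is affected. It is not: the arm comparison is tested separately under Hypothesis 1. A reader might also count the general statement in Background item f as a power claim for these factors, but it names none. The Problem section makes a sample-size statement, not a power claim.

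**What to change.** - **Selection.** Delete the sentence that includes or excludes factors by significance. Fit one prespecified logistic model with arm and all listed factors, keep the parameters few, state the speech-language coding and name the test. With about 3 events per parameter, Firth penalisation is preferable: for a true odds ratio of 2, the median over all results is 1.93-2.00, against 2.26-2.43 unpenalised. Firth alone does not cure selection (significant binary results still have medians of 4.8-5.9), so reporting every factor is the essential step.
- **Reporting.** Give every odds ratio with its 95% confidence interval as exploratory. Add to Hypothesis 5 that non-significance will not be read as evidence of no effect.
- **Outcome.** Use one definition in the third objective, Hypothesis 5 and the analysis plan: loss of the primary SAD and/or SM diagnosis at T3.
- **Power claim.** Remove or qualify it in Risk Factors, along with the matching sample-size statements in Problem and Feasibility of the Study. Give any detectable odds ratios only as illustrations under stated assumptions.

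The cost is wording and a standard regression, with no new data. The intervals will be wide and Hypothesis 5 will claim less. With Firth, Wald power at an odds ratio of 2 falls from 18-25% to 14-18% (binary) and from 51-62% to 40-53% (continuous).
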